Attention Control Condition: Participants randomized to the control condition will receive access only to the Resource Locator embedded within iReach. While the provision of a service locator is a form (albeit weak) of an intervention and may decrease our ability to detect intervention effects, we felt that withholding referrals to services would be unethical given AMSM's vulnerability to HIV and STIs. By providing the existing testing site locator only, we will still be able to test the effect of iReach (i.e., user-tailored content focused on life skills + peer mentor counseling through VSee). Participants initially randomized into the control condition will receive three months of access to the full intervention after they have completed 12 months in the control condition.

Additionally, during months 12 to 15 of participation, we will test whether incentivization of app engagement has any effect on participant utilization of intervention features. Participants initially randomized to the control condition, upon completing 12 months in the attention control condition and receiving three months access to the full intervention, will be informed that they can earn an additional \$40 reward for earning badges totaling 25 points in the iReach app (see image of point system below). See page 14 of this document for a description of iReach badges. Participants will be able to choose which badges they want to pursue, and therefore will be able to choose which intervention actions they complete in order to earn the incentive. Badges are set up to reward incremental use of app features (e.g. badge 1 = read one page, badge 2 = read five pages, etc.). We have developed the point system and chosen the target of 25 points so as to reward moderate use of the app, use which requires meaningful but achievable use. Participants who reach the 25 point target during their three months of full intervention access will earn an additional \$40 Amazon gift card, paid after the completion of the 15 month survey (or timing out of the survey window).

2. Data Collection:

Data will be collected from participants through web surveys at baseline, month 3, month 6, month 9, and month 12 (and month 15 for participants initially randomized into the control condition). For participants who engage in peer mentoring sessions with peer mentors, information about the session will be documented at the time of the session.

3. Genetic Testing:

Not applicable.

4. Use of Deception:

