Not applicable.

5. Statistical Analysis:

Descriptive statistics of the psychosocial and demographic characteristics of the participants will be described for all and by intervention group. These will be compared between treatment groups using t-tests or Wilcoxon rank sum tests for continuous variables and chi-square tests for categorical variables. In addition, we will use the general framework of generalized linear mixed models (GLMM) to test for intervention effects over time. Note that some of our outcomes are binary, some count and some continuous traits and thus need to be treated differently. The general form of the GLMM will be $\mu_{ij} = \beta_0 + \beta_1 \text{cov} + \beta_2 \text{Time} + \beta_3 \text{InterventionGroup} + \beta_4 \text{Group} \times \text{Time}$, where μ_{ij} is the mean response corresponding to subject i at Time j (baseline and 4 follow-ups) with the appropriate link function (identity for continuous outcome, logit for binary outcome and natural log for count outcomes); Group = 1 if the i -th subject is in the intervention group and 0 if the i -th subject is in the attention-control group. The interaction coefficients β_4 (Group \times Time) are of interest here, measuring the difference in the rate of change in outcomes across the two treatment groups over time. The subject-specific random intercepts β_0i are assumed to be normally distributed with a common variance and they account for within-person correlation. We will also explore if we need a subject specific random-slope corresponding to visit in the above model. Maximum likelihood estimation will be used for fixed effect parameters. Models will be compared according to information criterion like AIC, BIC. For some binary outcomes like HIV testing, we will perform an aggregate analysis after collapsing across the repeated measures using simple logistic regression comparing whether the probability of having tested at least once over the entire FU period is different across treatment groups, after adjusting for baseline values. To ensure robustness, we will also apply an exchangeable working correlation structure to its corresponding generalized estimating equation (GEE) model. We will also conduct exploratory regression analyses to examine differences based on social determinants of interest: age group, race/ethnicity, and rurality. These regressions will be run with group assignment and the social determinant variables of interest in the models, controlling for region. Interactions between group assignment and these social determinants will be tested to explore potential group-specific moderators of treatment effect. Given our focus on disparities, we also intend to examine mean differences across sub-groups of interest (e.g., race/ethnicity, developmental age group, urban vs. suburban vs. rural). For example, assuming we used a fixed effects ANOVA model with main effects and interactions by race and intervention condition, we would be able to detect any interaction effect size f of .18 in cross-sectional analyses at 80% power using a two-sided significance level of .05. Similar interaction effect sizes are obtained for developmental age (i.e., early (ages 13-14) vs. middle (ages 15-16) vs. late (ages 17-18) adolescence) and rurality (i.e., urban vs. sub-urban vs. rural). Secondary Analyses: Building on our GLMM framework employed for Aim 2, we will examine whether there are intervention effects in the socioecological factors (e.g., LGBT discrimination; HIV stigma) and life skills components (e.g., personal competence; identity development) associated with our outcomes. The regressions will be run with group assignment only in the model, as well as controlling for participants socio-demographic characteristics, psychological distress, and intervention-related process data (e.g., frequency of use, acceptability). In addition, we will test whether these relationships vary as a function of AMSMs varying engagement with the intervention (e.g., dose analysis; intervention acceptability, frequency of site log-ins; time spent on sites and modules; number and length of VSee sessions used). Interactions between group assignment and these characteristics will be tested to explore potential moderators of treatment effect. Recognizing that social determinants operate beyond the individual-level, we will use HLM to test how regional characteristics influence AMSMs outcomes. HLM allows us to take into account that participants are nested within regions, and examine whether regional characteristics are associated with individual-level outcomes. We will link individual and regional level data using participants residential address at enrollment. Some participants may be residentially unstable and/or would not want to give their exact location. We will estimate a two-level model to account for individual and regional variation.

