participation of the respondent, such that the respondent is aware of the nature of the questions to be included in the surveys. The study website will provide these details in full, during the consent process, and once the participant has created their password protected profile they will be able to access full information on the expectations of participation and the types of questions they will be asked. Informed consent documents will inform research participants of the need to keep answers to questions confidential. Participants will have the option to refuse to answer or skip any questions on the surveys that they are uncomfortable answering. 2) Psychological distress is a potential risk to AMSM during the completion of the surveys, reading the intervention content and during the teleconference counseling. We will provide AMSM with information to allow them to contact crisis services at the National Runaway Safeline at any time if they experience psychological distress, and the ability to contact the study team if they experience any adverse effects related to participation in the study. If psychological distress is apparent during a tele-conference, our licensed clinicians will be available to talk with the participant. In addition, we will refer crisis cases to the National Runaway Safeline which is available 24 hours a day, 7 days a week. In consultations with the leadership of the National Runaway Safeline, it was determined that crisis line staff would not need study-specific training in order to provide quality crisis support services to study participants, and actually might complicate the process. National Runaway Safeline staff are trained in providing crisis counseling to this age group, including sexual and gender minority youth. Research staff will receive training in crisis assessment and management procedures in the unlikely event that participants reveal suicidal and/or homicidal ideation, or child physical/sexual abuse. We will use established protocols from our prior studies conducted with youth and MSM for research staff to guide them in responding to crisis or harm situations, including attempting to contact the participant to assess risk level and provide appropriate follow-up (e.g., crisis hotline, safety check, suicide hotline). We will notify participants when we must engage in mandatory reporting during the consent process and when the participant decides to share a reportable event with study staff. 3) Unintended disclosure is also a potential risk. Given parents potential to monitor what apps their children have downloaded on their phones, we opted to keep iReach as a mobile-friendly WebApp. As a result, only individuals who know the URL can access the site. Participants will be instructed at different moments during the study (e.g., screening, baseline, followup) of steps they can take to further protect their privacy (e.g., clear browser history; avoid saving username/password in browser; logging out every time; using the app in private; using a screen lock on their phones, if parents allow). In addition, to limit inadvertent disclosure of their participation in the study to parents or others, we will suggest that youth create strong passwords (mix of upper/lower case letters, numbers, or symbols) on their iReach and personal e-mail accounts. Further, youth will choose how they wish to be contacted by the study staff (e.g., email, text message, private message on Facebook), and none of these exchanges will include sensitive information about HIV/STI, MSM, or anything that may reveal their participation in a study or answers to any of the questions answered in the surveys. Participants will be asked to provide at least two forms of contact information. Because participants are providing these pieces of identifiable information, there is a possibility that their participation in a research study could be disclosed in the following ways: (1) if someone other than the participant sees the intervention content; (2) if someone besides the participant reads the email sent with the link to the follow-up survey in which participants will enter their results; or (3) if someone besides the participant sees the study text messages, or online surveys on participants computer, tablet or phone. The risk of disclosure of participation in a research study through receiving study related emails, receiving text messages, interacting with the online surveys or with the study application on the participants cell phone will be minimized in the following ways: (1) participants must always log-in to re-enter the site after periods of inactivity as a fail-safe to avoid unintended disclosure; (2) emails with a link to the study follow-up surveys will not make any reference to the nature of the survey; for online surveys, participants will be required to login to the study website with the username and password that they created as part of the registration process before beginning the baseline survey; (3) participants will be encouraged to delete any text messages received as part of the study to protect them from an unauthorized individual viewing the messages, and to interact with the study application when in private (e.g., screen lock, complete when alone). Participants will be notified of these risks in the consent process. 4) One potential challenge is the security and confidentiality of VSee. Unlike other video-chat platforms (e.g. Skype), VSee is HIPAA-compliant and will be used for the peer mentoring sessions. Participants will have the option to use VSee in several formats: face-to-face video chat, video chat in which they can see the peer mentor but the peer mentor cannot see them, audio chat only, or a text based conversation. The consent form will include a full description of VSee, their options for using VSee, and will also make it clear that they can opt to have as many or few VSee sessions they wish (after the introductory session). Participants will request a VSee session through the iReach WebApp: when requesting a VSee session participants will be able to indicate the format they would like the session to take (e.g. face to face or audio only). VSee is compatible on PCs, tablets and smartphones. VSee includes the following functions to protect users: - End-to-end encryption without a man-in-the-middle listener. In WebEx, Vidyo, Tandberg, and Polycom architectures, your media is sent to a server (also called a video relay or MCU). Although encryption is applied from the users computer to these servers, the servers still have full access to the users media. In contrast, VSee uses end-to-end encryption where no server, including VSee servers, has the decryption key. VSee uses public/private RSA keys to exchange a 256-bit AES session key with the property that only the endpoints have the AES session key. VSee uses FIPS 140-2 certified 256-bit AES encryption. - One port. H.323 systems not only require many ports, but they require dynamic ports. This means if you want to use H.323 across your firewall, you are essentially opening your network to attackers on many ports. VSee, on the other hand, uses a single port for call signaling and media. The VSee protocol is structured so that only the outgoing port needs to be open because return traffic is always structured as responses to outgoing traffic. This allows administrators to set a policy where if users

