
Pennsylvania, Emory University, and the University of Michigan. Breaks in confidentiality will occur in the event that a participant is a danger to him or herself or to others, or is in danger from others. We will report this in accordance with rules for mandatory reporting. There is a statement in the consent form and assent form notifying participants of this possibility. All study personnel will have either completed the Human Subject Training established by the CITI program, or the comparable training required by their home institution. In addition, in compliance with the NIH policy, University graduate students and staff will participate in at least 8 hours of mandatory case study and discussions regarding scientific integrity and human subjects. Any additional personnel who may join the project will complete this training before they handle any subject data. Further, issues regarding confidentiality will be reinforced prior to each intervention and data collection with project personnel. Reporting Adverse Events Additionally, all staff will be trained on recognition and documentation of any unusual events or circumstances that occur during data collection. Staff will be trained to report any adverse events that concern them immediately to the Principal Investigators and the University IRB. If an adverse event appears to be research-related, it will be reported to the OHRP and the funding institution project officer, along with summaries of discussions concerning the event. The funding institution project officer will be informed of any IRB action taken concerning any adverse event. The Principal Investigators and Project Director will monitor staff closely. Staff deficient in any aspect of performance will be re-trained, closely monitored for proficiency, and if not adhering to established protocols and procedures, will be terminated. When data are collected via Alchemer, they are automatically encrypted, with the coded access only available to the Project Director and the PIs. No names or other identifying information appear on data documents or in data files as the re-contact information will be stored separately. Only designated staff will have access to the data. The Principal Investigators and Co-Investigators will be responsible for dissemination of study findings through presentations and publications. The Principal Investigators will also be solely responsible for handling any requests from other investigators to examine the data collected during this study.

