Secondary outcomes: changes in sexual behavior and change in HIV testing behavior over the 12-month follow-up period. **Sexual risk behavior** will be assessed using the Sexual Practices Assessment Schedule for Youths. We have adapted this assessment for use in previous online studies with YMSM. The assessments ask lifetime of sexual partners and types of sexual acts (e.g., kissing, touching, oral sex, penetrative sex) before proceeding any further. For behaviors reported, the assessment then explores the number of occasions of different sexual acts (oral, anal; receptive, insertive) with three different types of partners (romantic interest, casual partner ["hookup"] or friend with benefits), use of condoms during the past 3 months, and knowledge about partners' HIV status. The assessment also differentiates between male and female partners. We will adapt the assessment to ascertain whether, to their knowledge, their sexual partners are on PrEP. **HIV/STI testing and care:** The baseline survey will include questions on lifetime HIV/STI testing history²⁷¹. Follow-up surveys will repeat the questions from the baseline and will also include questions on HIV/STI testing in each 3-month period including test results. Among newly diagnosed HIV+ cases, we will assess their linkage and retention in care.

Study Methods

General Study Design and Plan

We will conduct a prospective RCT of 600 online-recruited cis-gender AMSM (age 13-18 years) followed for 12 months with study assessments at each 3-month interval. A racially/ethnically diverse sample (at least 50% racial/ethnic minority) of AMSM living in four regions in the United States: (1) Chicago, IL to Detroit, MI; (2) Washington, DC to Atlanta, GA; (3) San Francisco, CA to San Diego, CA; and (4) Memphis, TN to New Orleans, LA. Regions were identified by inspection of HIV prevalence rate maps on AIDSVu.org. Eligible counties are those that include the major interstate highway that connects the two anchor cities (ie, I-94 for Chicago to Detroit; I-95 for Washington, DC to Atlanta; I-5 for San Francisco to San Diego; and I-55 from Memphis to New Orleans). Each region includes urban, suburban, and rural counties, as classified by the 2006 National Center for Health Statistics urban-rural classification scheme for counties [15].

Inclusion-Exclusion Criteria and General Study Population

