We will also collect information of the following mediators and moderators for our analyses: Socio-demographic information will include questions on race/ethnicity, educational attainment, employment status, place of birth, year of immigration (when appropriate), housing status, history of incarceration, and engagement in transactional sex. Psychological distress will be measured using existing, well-validated scales. We will use subscales from the Brief Symptom Inventory to measure depressive symptoms and anxiety symptoms. Depressive symptoms include 6 items ($\alpha > .80$) rated on a 5-point scale (1=never, 5 = very often). Items include feelings of loneliness, blue or sad, and having thoughts of ending one's life. Anxiety also includes 6 items ($\alpha > .90$) measured on the same 5-point scale and includes reporting nervousness or shakiness, feeling fearful, or suddenly scared for no reason. We will also measure AMSM's Perceived Loneliness using the UCLA Loneliness Scale using a 4-point scale (1=Never;4=Often). In our prior work, reliability for this scale with YMSM was high ($\alpha > .90$). To measure Stress, we will assess perceived stress through daily hassles. AMSM will rate their experiences of stress over the past month (e.g., how often have you found that you could not deal with all the things that you had to do), and rate the frequency with which they felt these ways on a scale from 1 (Never) to 5 (Very often). We have used these measures in prior studies and have shown excellent psychometric properties consistently over time. Social Media Use: Given potential disparities in access to technology, we will include the PEW Internet Survey questions regarding use of different devices, the number of hours spent online through each device, the reasons for social media use, sites commonly frequented, and extent to which the Internet supplements face-to-face interactions. We will also measure AMSM's frequency of use of social media to look for HIV or sexual health-related information, and their online partner-seeking behaviors. Online health seeking competency will be measured using an adapted, 6-item version of the eHealth Literacy Scale (eHEALS) that asks respondents on a 5-point Likert scale about their knowledge of online resources including where to locate them, how to find them, how to use information, and comfort with assessing the quality of online health information.

Missing Data

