Analysis tests the efficacy of the iREACH intervention as compared to a delayed intervention condition, to create positive changes in the following outcomes: *primary outcomes*: changes in confidence to engage in HIV prevention behaviors and changes in HIV knowledge and *secondary outcomes*: changes in sexual behavior and change in HIV testing behavior over the 12-month follow-up period. Descriptive statistics of the behavioral, psychosocial, and demographic characteristics of the participants will be described for all and by group (intervention and control). These will be compared between treatment groups using t-tests or Wilcoxon rank sum tests for continuous variables and chi-square tests for categorical variables. In addition, we will use the general framework of generalized linear mixed models (GLMM) to test for intervention effects over time. Note that some of our outcomes are binary, some count and some continuous traits and thus need to be treated differently. The general form of the GLMM will be $(\mu_{ij}) = \beta_{0i} + \beta_{\text{cov Covariates}_{ij}} + \beta_{\text{Time}_{j}} + \beta_{\text{Intervention Group}_i} + \beta_{\text{Group} \times \text{Time}_i}$, where μ_{ij} is the mean response corresponding to subject i at Time j (baseline and 4 follow-ups) with the appropriate link function (identity for continuous outcome, logit for binary outcome and natural log for count outcomes); Group =1 if the i -th subject is in the intervention group and 0 if the i -th subject is in the attention-control group. The interaction coefficients $\beta_{\text{Group} \times \text{Time}}$ are of interest here, measuring the difference in the rate of change in outcomes across the two treatment groups over time in the primary and secondary outcomes. Models will be compared according to information criterion like AIC, BIC. For some binary outcomes like HIV testing, we will perform an aggregate analysis after collapsing across the repeated measures using simple logistic regression comparing whether the probability of having tested at least once over the entire FU period is different across treatment groups, after adjusting for baseline values. To ensure robustness, we will also apply an exchangeable working correlation structure to its corresponding generalized estimating equation (GEE) model.

Reporting Conventions

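### The documents disagree on whether depression and anxiety are secondary outcomes or covariates, so a randomised comparison of a harm the protocol itself names is not assured

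*SAP*

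**What the plan says.** The protocol's Risk/Benefit Assessment (Risks, item 2) states: "Psychological distress is a potential risk to AMSM during the completion of the surveys, reading the intervention content and during the teleconference counseling". Surveys are common to both arms. Content and counselling are not: under Attention Control Condition, "Participants randomized to the control condition will receive access only to the Resource Locator embedded within iReach", with full access opening only after month 12.

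On measurement, the SAP (Covariates and Subgroups) says: "We will use subscales from the Brief Symptom Inventory to measure depressive symptoms and anxiety symptoms". The depression subscale has six items rated 1 to 5, one of them on suicidal thoughts. The SAP's schedule table marks Depression and Anxiety at baseline and months 6, 12 and 15. The protocol (Subject Follow-up) makes month 15 a control-arm survey, so between-arm data exist at baseline, month 6 and month 12.

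The role given to these scales varies:

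- **SAP, schedule table:** both appear in the secondary-outcomes block, apart from the table's own covariates block.
- **SAP, Covariates and Subgroups:** distress falls under the sentence "We will also collect information of the following mediators and moderators for our analyses".
- **SAP, Endpoints:** "Secondary outcomes: changes in sexual behavior and change in HIV testing behavior over the 12-month follow-up period". Efficacy Analyses repeats the same two domains.
- **Protocol, Study Instruments:** the secondary outcomes are sexual risk, substance use and linkage to prevention services; distress comes later, under covariates.
- **Protocol, Statistical Analysis (Secondary Analyses):** some models are run "controlling for participants socio-demographic characteristics, psychological distress, and intervention-related process data".

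For adverse events, the protocol's Data and Safety Monitoring section says: "Staff will be trained to report any adverse events that concern them immediately to the Principal Investigators and the University IRB". The SAP has no safety section.

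**The concern.** A named harm in 13- to 18-year-olds is measured in a randomised trial, but the plan never states plainly that it will be compared between arms. An analyst who follows the schedule table would fit an arm comparison. One who follows the Endpoints and Covariates text could enter distress on the right-hand side of a model and report no effect on it. Either would be following the documents.

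Two consequences follow. First, the protocol's judgement that benefits clearly exceed risks might not be checked against the trial's own randomised data. Second, if post-randomisation distress is used as a covariate in a model of the intervention effect, any part of the effect that acts through distress can be adjusted out.

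The suicidal-thoughts item is a separate matter. It is one of six items in a subscale score, and a rise confined to it could be diluted in the scale mean. Neither document plans a tabulation of it.

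**Working it through.** The plan gives no figure for distress, so there is none to reproduce. The check is a reading of the text, followed by a calculation of what the comparison could show.

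**1. Does any text commit to an arm comparison?**

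Efficacy Analyses says the Group × Time term measures the arm difference in the primary and secondary outcomes. Everything turns on which outcomes those are.

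- *Reading A:* they are the schedule table's secondary block. Depression and anxiety are then compared by arm.
- *Reading B:* they are the outcomes listed at the start of the same section, "changes in sexual behavior and change in HIV testing behavior over the 12-month follow-up period". Depression and anxiety are then not compared.

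The table cannot settle this alone, because its headings depart from the endpoint text elsewhere. It puts HIV/STI testing under primary outcomes, while Endpoints and Efficacy Analyses make HIV testing secondary. The short lists cannot settle it either. They omit substance use and PrEP use, which the table lists as secondary and the protocol describes under secondary outcomes. Both readings remain open.

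**2. How could distress enter as a covariate?**

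The SAP's model indexes covariates by subject and time (i and j). Nothing limits distress to its baseline value. Equally, nothing says a post-baseline value will be used.

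**3. What could the comparison detect?**

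Inputs: 250 completers per arm (SAP, Randomization and Blinding); two-sided 0.05, 80% power and within-person correlations of 0.25 and 0.75 (SAP, Sample Size). Those correlations are not given for the Brief Symptom Inventory; applying them here is an assumption.

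Unadjusted: (1.960 + 0.842) × √(2/250) = 0.251 SD.

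Adjusted for the baseline score: (1.960 + 0.842) × √(2(1 − ρ²)/250)

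- ρ = 0.25: 2.802 × √0.0075 = 0.243 SD
- ρ = 0.75: 2.802 × √0.0035 = 0.166 SD

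The SAP's stated d = 0.22 concerns the cognitive outcomes and is not used here.

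**4. The suicidal-thoughts item**

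The documents give neither an endorsement rate nor a cut-point on the 1-to-5 rating, so the rates below are assumed. The 95% CI half-width for the arm difference is 1.96 × √(2p(1 − p)/250). The last column is the increase over the assumed control rate that is detectable at 80% power, two-sided 0.05, 250 per arm.

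| Assumed rate | CI half-width (points) | Detectable increase (points) |
|---|---|---|
| 5% | – | 7.0 |
| 10% | 5.3 | 8.8 |
| 20% | 7.0 | 10.9 |
| 30% | 8.0 | 12.0 |

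The scale means would be compared with useful precision. The single item would be described, but small increases could be missed.

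**The case against.** The strongest reply is that the comparison is already planned: the table calls both scales secondary outcomes, and Efficacy Analyses applies Group × Time to the secondary outcomes. A reader might infer from the Endpoints and Covariates text alone that no arm contrast is planned. The documents do not support that, because Reading A is fair. It is not the only fair reading, however, and an analysis of harm should not depend on which section the analyst opens.

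A reader might also infer that a rise in distress would go unreported. That goes too far. Summary of Study Data plans summaries of all continuous variables and tables with a column per treatment. Efficacy Analyses describes and tests psychosocial characteristics by group, without a time point and possibly at baseline only. By-arm means may therefore appear. These passages do not commit the trial to a post-baseline difference with a confidence interval.

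Nor are staff-noticed events the only other harm information. Participants in both arms can report adverse effects to the study team, crisis procedures exist, and research-related events go beyond the IRB to federal oversight and the funder. These are routes for individual cases; no by-arm tabulation is stated. The documents do not propose comparing event rates, so no biased comparison can be charged to them. The difference in staff contact is a caution for whoever reads a by-arm listing.

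On adjustment, the protocol's Secondary Analyses also run models with group assignment alone, and they concern socioecological and life-skills factors rather than the primary outcomes. Adjusting out an effect is therefore a possibility left open, not a stated plan.

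Two limits stand. Scales at months 6 and 12 may miss transient distress during a session. The protocol also classes the study as no more than minimal risk, which bears on urgency but does not resolve the contradiction.

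**Conclusion.** The concern holds as an internal contradiction with a consequence for safety reporting. Depression and anxiety are secondary outcomes in one place, covariates, mediators or moderators in others, and missing from the named secondary outcomes in both documents. With no safety analysis in the SAP, a randomised comparison of a named harm may not be reported, although the scores are scheduled in both arms.

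If made, the comparison could detect about 0.17 to 0.24 SD on each scale with 250 per arm, provided the plan's correlations of 0.25 to 0.75 apply to these scales. For the suicidal-thoughts item, CI half-widths would be about 5 to 8 points at assumed rates of 10% to 30%. These figures describe what the data could show; they do not estimate any harm. The amendment is worth making because it settles, before results are seen, how a named risk will be read.

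**What to change.** - Reconcile the SAP (Endpoints, schedule table, Covariates and Subgroups, Efficacy Analyses) with the protocol (Study Instruments, Statistical Analysis) by naming depressive and anxiety symptoms as secondary (safety) outcomes, read in both directions.
- Report the iReach-minus-control difference on each scale at months 6 and 12 with a 95% CI, adjusted for the baseline score. Leave month 15 out of the comparison, since only controls are surveyed then.
- Report the suicidal-thoughts item by arm, either as its full response distribution or as a proportion above a cut-point stated in advance.
- Where distress stays as a covariate in effect models, use the baseline value only.
- List adverse events by arm, with a note that staff contact differs between arms through mentor sessions and the monitored forum.

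The cost is SAP and protocol wording plus a few model fits and tables on data already scheduled for collection. No clinical procedure changes. The downside is one more reported domain, which should be labelled as safety and kept outside the efficacy claims.
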